11.3 Response Criteria

11.3.1 Evaluation of Target Lesions

Complete Response (CR): Disappearance of all target lesions. Any pathological lymph nodes (whether target or non-target) must have reduction in short axis to <10 mm.

Partial Response (PR):	At least a 30% decrease in the sum of the diameters of target lesions, taking as reference the baseline sum of diameters.
Progressive Disease (PD) :	At least a 20% increase in the sum of the diameters of target lesions, taking as reference the smallest sum on study (this includes the baseline sum if that is the smallest on study). In addition to the relative increase of 20%, the sum must also demonstrate an absolute increase of at least 5 mm. (Note: the appearance of one or more new lesions is also considered progressions).
Stable Disease (SD) :	Neither sufficient shrinkage to qualify for PR nor sufficient increase to qualify for PD, taking as reference the smallest sum of diameters while on study.

11.3.2 Evaluation of Non-Target Lesions

Complete Response (CR):	Disappearance of all non-target lesions and normalization of tumor marker level. All lymph nodes must be non-pathological in size (<10 mm short axis).		
	Note: If tumor markers are initially above the upper normal limit, they must normalize for a patient to be considered in complete clinical response.		
Non-CR/Non-PD:	Persistence of one or more non-target lesion(s) and/or maintenance of tumor marker level above the normal limits.		
Progressive Disease (PD):	Appearance of one or more new lesions and/or unequivocal progression of existing non-target lesions. Unequivocal progression should not normally trump target lesion status. It must be representative of overall disease status change, not a single lesion increase.		

Although a clear progression of "non-target" lesions only is exceptional, the opinion of the treating physician should prevail in such circumstances, and the progression status should be confirmed at a later time by the review panel (or Principal Investigator).

11.3.3 Evaluation of Best Overall Response

The best overall response is the best response recorded from the start of the treatment until disease progression/recurrence (taking as reference for progressive disease the smallest measurements recorded since the treatment started). The patient's best response assignment will depend on the achievement of both measurement and confirmation criteria.

Target Lesions	Non-Target	Non-Target New Overa		Best Overall Response when				
	Lesions	Lesions	Response	Confirmation is Required [*]				
CR	CR	No	CR	24 wks. Confirmation**				
CR	Non-CR/Non-PD	No	PR					
CR	Not evaluated	No	PR	Multa Confirmation**				
PR	Non-CR/Non-	No	PR	≥ 4 wks. Commination				
	PD/not evaluated							
SD	SD Non-CR/Non-		SD	Documented at least once > 4				
	PD/not evaluated			wks. from baseline**				
PD	Any	Yes or	PD					
		No						
Any	PD***	Yes or	PD	no prior SD, PR or CR				
2		No						
Any	Any	Yes	PD					
* See RECIS	See RECIST 1.1 manuscript for further details on what is evidence of a new lesion.							
** Only for no	* Only for non-randomized trials with response as primary endpoint.							
*** In exception	** In exceptional circumstances unequivocal progression in non-target lesions may be accepted as							

*** Only for non-randomized trials with response as primary endpoint.
 *** In exceptional circumstances, unequivocal progression in non-target lesions may be accepted a disease progression.

For Patients with Non-Measurable Disease (i.e., Non-Target Disease)

Non-Target Lesions	New Lesions	Overall Response					
CR	No	CR					
Non-CR/non-PD	No	Non-CR/non-PD*					
Not all evaluated	No	not evaluated					
Unequivocal PD	Yes or No	PD					
Any	Yes	PD					
* 'Non-CR/non-PD' is preferred over 'stable disease' for non-target disease since SD is increasingly							
used as an endpoint for assessment of efficacy in some trials so to assign this category when no							
lesions can be measured is not advised							

Note: Patients with a global deterioration of health status requiring discontinuation of treatment without objective evidence of disease progression at that time should be reported as *"symptomatic deterioration."* Every effort should be made to document the objective progression even after discontinuation of treatment.

11.4 Duration of Response

Duration of overall response: The duration of overall response is measured from the time measurement criteria are met for CR or PR (whichever is first recorded) until the first date that recurrent or progressive disease is objectively documented (taking as reference for progressive disease the smallest measurements recorded since the treatment started).

The duration of overall CR is measured from the time measurement criteria are first met for CR until the first date that progressive disease is objectively documented.

Duration of stable disease: Stable disease is measured from the start of the treatment until the criteria for progression are met, taking as reference the smallest measurements recorded since the treatment started, including the baseline measurements.

12 DATA REPORTING / REGULATORY REQUIREMENTS

Adverse event lists, guidelines, and instructions for AE reporting can be found in Section 7.0 (Adverse Events: List and Reporting Requirements).

12.1 Data Reporting

12.1.1 Method

This study will be monitored by the Clinical Trials Monitoring Service (CTMS). Data will be collected in the Center for Cancer Research C3D database and will be transmitted to CTMS electronically at least once every 2 weeks.

Note: All adverse events that have occurred on the study, including those reported through CTEP-AERS, must be reported via the monitoring method identified above.

12.1.2 Responsibility for Data Submission

N/A

12.2 CTEP Multicenter Guideline

N/A

12.3 Collaborative Agreements Language

The agent(s) supplied by CTEP, DCTD, NCI used in this protocol is/are provided to the NCI under a Collaborative Agreement (CRADA, CTA, CSA) between the Pharmaceutical Company(ies) (hereinafter referred to as "Collaborator(s)") and the NCI Division of Cancer Treatment and Diagnosis. Therefore, the following obligations/guidelines, in addition to the provisions in the "Intellectual Property Option to

Collaborator" (http://ctep.cancer.gov/industryCollaborations2/intellectual_property.htm) contained within the terms of award, apply to the use of the Agent(s) in this study:

- 12.3.1 Agent(s) may not be used for any purpose outside the scope of this protocol, nor can Agent(s) be transferred or licensed to any party not participating in the clinical study. Collaborator(s) data for Agent(s) are confidential and proprietary to Collaborator(s) and shall be maintained as such by the investigators. The protocol documents for studies utilizing Agents contain confidential information and should not be shared or distributed without the permission of the NCI. If a copy of this protocol is requested by a patient or patient's family member participating on the study, the individual should sign a confidentiality agreement. A suitable model agreement can be downloaded from: http://ctep.cancer.gov.
- 12.3.2 For a clinical protocol where there is an investigational Agent used in combination with (an)other Agent(s), each the subject of different Collaborative Agreements, the access to and use of data by each Collaborator shall be as follows (data pertaining to such combination use shall hereinafter be referred to as "Multi-Party Data"):
- **12.3.3** a. NCI will provide all Collaborators with prior written notice regarding the existence and nature of any agreements governing their collaboration with NCI, the design of the proposed combination protocol, and the existence of any obligations that would tend to restrict NCI's participation in the proposed combination protocol.

b. Each Collaborator shall agree to permit use of the Multi-Party Data from the clinical trial by any other Collaborator solely to the extent necessary to allow said other Collaborator to develop, obtain regulatory approval or commercialize its own Agent.

c. Any Collaborator having the right to use the Multi-Party Data from these trials must agree in writing prior to the commencement of the trials that it will use the Multi-Party Data solely for development, regulatory approval, and commercialization of its own Agent.

12.3.4 Clinical Trial Data and Results and Raw Data developed under a Collaborative Agreement will be made available to Collaborator(s), the NCI, and the FDA, as appropriate and unless additional disclosure is required by law or court order as described in the IP Option to Collaborator (http://ctep.cancer.gov/industryCollaborations2/intellectual_property.htm). Additionally, all Clinical Data and Results and Raw Data will be collected, used and disclosed consistent with all applicable federal statutes and regulations for the protection of human subjects, including, if applicable, the Standards for Privacy of Individually Identifiable Health Information set forth in 45 C.F.R. Part 164.

- **12.3.5** When a Collaborator wishes to initiate a data request, the request should first be sent to the NCI, who will then notify the appropriate investigators (Group Chair for Cooperative Group studies, or PI for other studies) of Collaborator's wish to contact them.
- **12.3.6** Any data provided to Collaborator(s) for Phase 3 studies must be in accordance with the guidelines and policies of the responsible Data Monitoring Committee (DMC), if there is a DMC for this clinical trial.
- 12.3.7 Any manuscripts reporting the results of this clinical trial must be provided to CTEP by the Group office for Cooperative Group studies or by the principal investigator for non-Cooperative Group studies for immediate delivery to Collaborator(s) for advisory review and comment prior to submission for publication. Collaborator(s) will have 30 days from the date of receipt for review. Collaborator shall have the right to request that publication be delayed for up to an additional 30 days in order to ensure that Collaborator's confidential and proprietary data, in addition to Collaborator(s)'s intellectual property rights, are protected. Copies of abstracts must be provided to CTEP for forwarding to Collaborator(s) for courtesy review as soon as possible and preferably at least three (3) days prior to submission, but in any case, prior to presentation at the meeting or publication in the proceedings. Press releases and other media presentations must also be forwarded to CTEP prior to release. Copies of any manuscript, abstract and/or press release/ media presentation should be sent to:

E-mail: [contact]

The Regulatory Affairs Branch will then distribute them to Collaborator(s). No publication, manuscript or other form of public disclosure shall contain any of Collaborator's confidential/ proprietary information.

12.4 Genomic Data Sharing Plan

The NIH Genomic Data Sharing (GDS) Policy does not apply to this protocol as we will be performing exploratory genetic analysis of no more than 26 patient samples; therefore, this study does not meet GDS criteria, and no GDS plan has been developed.

13 STATISTICAL CONSIDERATIONS

13.1 Study Design/Endpoints

13.1.1 Primary Endpoints

The primary objectives are:

- To establish the safety and tolerability of single agent AZD1775 in patients with refractory solid tumors.
- To determine the pharmacokinetics of AZD1775 in patients with refractory

solid tumors.

13.1.2 Secondary Endpoint

The secondary objective is:

- To evaluate the antitumor activity of AZD1775 in patients with refractory solid tumors.
- **13.1.3** Exploratory Endpoints

The exploratory objectives are:

- To determine the effect of AZD1775 on pharmacodynamic markers of DNA damage and apoptosis in tumor tissue and blood.
- To assess whether sufficient Weel inhibition is maintained throughout the therapeutic regimen.
- To identify tumor genomic alterations and gene expression patterns potentially associated with AZD1775 antitumor activity.

13.2 Study Design

This Phase I study will use a standard 3+3 design, and permits intra-patient dose modification (defined in Section 5.1). The MTD or recommended Phase II dose is the dose level at which no more than 1 of 6 patients experience DLT during the first cycle of treatment, and the dose below that at which at least 2 (of < 6) patients have DLT as a result of the drug.

13.3 Sample Size/Accrual Rate

With Amendment E (dated 09/24/2013), an additional expansion arm of 6 patients with documented tumors harboring BRCA-1 or-2 mutations will also be enrolled at the MTD to further explore the safety of AZD1775 and obtain preliminary evidence of activity in this patient population. This information may inform patient selection for further development of this agent.

With Amendment G (dated 07/17/2014) an additional Arm B will be established to further evaluate an alternative once-daily dosing schedule. Patients will be enrolled based on the standard 3+3 design. Once the maximum tolerated daily dosing is established, up to 20 additional patients will be enrolled at this dose to further evaluate PD endpoints. With that number, and a tumor biopsy QA criteria failure rate of 40% with respect to paired (pre- and post-dose) biopsies, we have an 87% likelihood of having at least 10 usable PD samples, and 94% likelihood of having at least 9 usable samples. Biopsy tissue quality will be monitored and accrual will stop once we have obtained 10 usable paired samples.

The study is a standard design using 3 patients per arm, unless DLT is noted, in which

point up to 6 patients may be enrolled in an arm. Up to 30 patients will be enrolled for determination of the MTD. In addition, an additional 6 patients will be enrolled at the MTD to further define the dose and evaluate PD studies at this dose level (Expansion Arm A). To allow for a small number of patients who may not be evaluable, and the addition of Arm B, the accrual ceiling for this trial is set at 72 patients. It is anticipated that 2-3 patients per month may be enrolled onto this study. Depending on the number of patients needed to reach MTD, it is expected that 24-48 months will be required to accrue the number of patients necessary to complete the trial.

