> Weel has additionally been shown to modulate the activity of the Mus81-Emel endonuclease complex responsible for cleavage of stalled replication forks by introduction of double stranded breaks to allow for replication recovery¹³. Massive induction of DNA breaks eventually overwhelms cellular capacity to repair the lesions, and as Weel inhibition also results in abrogation of the G2 checkpoint, cells are pushed towards mitotic lethality secondary to inability to repair damaged DNA. Based on these recent data demonstrating the role of Weel in maintenance of genomic integrity, we propose that AZD1775 may have single agent activity.

15

Non-Clinical Pharmacokinetics

Metabolism

Non-clinical toxicology

At the time of Amendment G, dated 07/17/2014, 18 patients have been enrolled onto Arm A of this study and the MTD established at 225 mg twice daily for 5 doses each week, for two consecutive weeks¹⁶. Confirmed partial responses were observed in two patients carrying BRCA mutations: one with head and neck cancer and one with ovarian cancer. As of Amendment I (dated 8/6/15), a total of 10 patients have been accrued to Arm B (qd dosing); this schedule has been well tolerated to date but persistent grade 2 nausea and vomiting on DL2 necessitated expansion to 6 patients to better define the toxicity. At the time of Amendment M (dated 11/20/16), a total of 24 patients have been accrued to Arm B, and we have established the Arm B MTD as DL4 (300 mg once daily on days 1-5 each week for two weeks).

Clinical Efficacy

Of 176 evaluable patients who received AZD1775 (either single or multiple doses) as monotherapy or in combination with gemcitabine, cisplatin, or carboplatin on Study PN001, a partial response (PR) (confirmed and unconfirmed) was observed in 17 (9.7%) patients, and stable disease (SD) was observed in 94 (53.4%) patients¹⁷. A phase II trial of AZD1775 in combination with carboplatin in patients with refractory or resistant TP53-mutated ovarian cancer (Study PN009) has also been performed, yielding a 43% overall response rate (partial response + complete response)¹⁸.

Safety

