Once the MTD is established, 6 additional patients will be enrolled at the MTD to further evaluate that dose for PK and PD endpoints (Expansion Arm A). An additional expansion arm of 6 patients with documented tumors harboring BRCA-1 or -2 mutations will also be enrolled at the MTD to further explore the safety of AZD1775 and obtain preliminary evidence of activity in this patient population. This information may inform patient selection for further development of this agent. Patients in this BRCA-mutant expansion arm must have measurable disease; tumor biopsies will be optional.

Based on preclinical data with once daily AZD1775 dosing, Arm B, starting at 200 mg once daily for 5 doses each week, for two consecutive weeks will be established to evaluate PD and PK endpoints. Patients will be accrued in arms of 3, based on a 3+3 design, for up to two dose levels. The cycle length will remain at 21 days (+ 1 day for scheduling). Once the maximum tolerated single daily dosing is established, up to 20 additional patients will be enrolled on Expansion Arm B with mandatory biopsies to further evaluate PD endpoints.

History and physical examination will be done at baseline (within 8 days prior to the start of protocol therapy) and before the start of each new cycle thereafter (up to 3 days before the start of a new cycle). Patients will be examined on D1 and D8 at the clinical center during the first cycle and prior to every new cycle.

As of Amendment G (dated 07/17/2014), the MTD for Arm A was established at 225 mg twice daily for 5 doses each week, for two consecutive weeks. As of Amendment M (dated 11/20/16), the Arm B MTD was established at 300 mg once daily on days 1-5 each week, for two consecutive weeks.

Labs (CBC with differential; serum chemistries) will be performed at baseline (within 8 days prior to the start of protocol therapy), D8, and D15 of cycle 1 (\pm 1 day due to scheduling conflicts), then at the start of each cycle (up to 3 days before start of a new cycle).

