The trial will follow a standard 3+3 dose escalation study wherein 3 patients should have completed at least one cycle of therapy prior to considering dose escalation in the next arm of patients. Dose escalation will proceed until dose-limiting toxicity is observed. DLT is defined in Section 5.2. Determination of DLT will be based on toxicities observed in the first cycle of therapy. Patients are considered evaluable for toxicity for the purpose of arm dose escalation decisions if they either 1) experienced DLT or 2) have received 90% of treatment doses for cycle one of therapy and have been followed for one full cycle without DLT. All toxicities will be reported for all patients who receive any amount of study drug on this study. Evaluation of toxicity will begin with study drug administration on cycle 1 day 1.

Intra-patient dose escalation will be permitted if: **a**) there is no toxicity > Grade 1 that is related (possibly, probably, or definitely) to the study drug at the initial dose level experienced by that patient, **b**) higher doses have been evaluated and completed without DLT, and **c**) the patient's disease has not progressed. Doses may be escalated, provided conditions a–c are met, up to the last evaluated dose level NOT associated with DLT.

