5.2 Definition of Dose-Limiting Toxicity

Determination of dose-limiting toxicity will be based on toxicities observed in the first cycle of therapy. Dose escalation will proceed within each arm according to the following scheme. Dose-limiting toxicity (DLT) is defined below.

Number of Patients with DLT at a Given Dose Level	Escalation Decision Rule
0 out of 3	Enter 3 patients at the next dose level.
≥2	Dose escalation will be stopped. This dose level will be declared the maximally administered dose (highest dose administered). Three (3) additional patients will be entered at the next lowest dose level if only 3 patients were treated previously at that dose.
1 out of 3	Enter at least 3 more patients at this dose level.If 0 of these 3 patients experience DLT, proceed to the next dose level.
	• If 1 or more of this group suffer DLT, then dose escalation is stopped, and this dose is declared the maximally administered dose. Three (3) additional patients will be entered at the next lowest dose level if only 3 patients were treated previously at that dose.
≤1 out of 6 at highest dose level below the maximally administered dose	This is generally the recommended phase 2 dose. At least 6 patients must be entered at the recommended phase 2 dose.

Dose limiting toxicity (DLT) is defined as an adverse event that is related (possibly, probably, or definitely) to administration of AZD1775 and fulfills one of the following criteria:

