5.2.1 Grade \geq 3 Non-Hematological Toxicity

Grade \geq 3 non-hematological toxicity felt to be related to study medications will be considered dose-limiting with the following clarifications:

5.2.1.1 Diarrhea Grade 3 will only be considered dose-limiting if it is refractory to treatment as outlined in Section 5.3.2, Supportive Care Guidelines, and unable to be corrected to Grade 2 or less within 24 hours. Bloody or Grade 4 diarrhea will be dose-limiting.

5.2.1.2 Nausea and vomiting Grade 3 will only be considered dose-limiting if it is refractory to anti-emetic therapy and unable to be corrected to Grade 1 or less within 24 hours (Section 5.3.1).

5.2.1.3 Rise in creatinine to Grade 3, not corrected to Grade 1 or less within 48 hours with IV fluids will be considered dose-limiting. All Grade 4 rises in creatinine will be dose limiting.

5.2.1.4 Grade \geq 3 metabolic toxicities unable to be corrected to Grade 1 or baseline within 48 hours (hypocalcemia or hypercalcemia, hypomagnesemia or hypermagnesemia, and hyponatremia) will be considered dose limiting. For hypokalemia or hyperkalemia, grade \geq 2 toxicities unable to be corrected to grade 1 or less within 48 hours will be considered dose limiting. Grade 4 metabolic toxicities that are symptomatic will be considered dose-limiting regardless of duration or ability to correct.

- **5.2.2** Grade 4 thrombocytopenia or Grade 3 thrombocytopenia associated with bleeding.
- **5.2.3** Grade 4 neutropenia \geq 5 days or febrile neutropenia.
- **5.2.4** Any degree of anemia, leukopenia in the absence of grade 4 neutropenia \geq 4 days, or lymphopenia will not be considered dose limiting.
- 5.2.5 Any degree of alopecia will not be considered dose limiting.
- 5.2.6 Grade 3 fatigue of greater than 1 week duration.
- 5.2.7 Failure to tolerate 100% of the dosing in the first cycle will be considered a DLT.

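### Expansion Arm B has no cumulative DLT count at which enrolment pauses for review; accrual ends only on biopsy yield or at the cap of 20

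*Combined protocol and SAP*

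**What the plan says.** Section 5 sets the size of the cohort: "up to 20 additional patients will be enrolled on Expansion Arm B with mandatory biopsies to further evaluate PD endpoints". Sections 9 and 13.3 both give the stopping condition: "Biopsy tissue quality will be monitored and accrual will stop once we have obtained 10 usable paired samples". Section 13.3 justifies the 20 by tissue yield, quoting 87% and 94% chances of at least 10 and at least 9 usable pairs at a 40% failure rate.

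The numeric DLT rules serve other decisions. The table in 5.2 governs escalation and stops it at 2 or more DLTs. Section 13.2 defines the MTD as the level where "no more than 1 of 6 patients experience DLT during the first cycle of treatment". Section 2.3 reports that "we have established the Arm B MTD as DL4", which is 300 mg once daily.

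Other safety provisions do reach expansion patients:
- holds and at most two dose reductions per patient (Section 6, 6.1)
- expedited SAE reporting to NCI, with listed exceptions (7.3.3)
- reports of unanticipated problems within 7 days (7.3.6)
- a tabulated AE summary at continuing review (7.4.1)
- data transfer to the monitoring service no less often than every two weeks (12.1.1)

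On blood counts, 5.3.3 lists only days 1 and 8 of cycle 1 for the expansion phase. Section 5 includes day 15, and footnote c of the Section 10 calendar asks for weekly counts in cycle 1. Neither exempts the expansion.

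**The concern.** Safety and tolerability are a primary objective, and six patients are thin evidence for a dose. Expansion Arm B is the larger cohort at that dose, so it is where a dose that passed by chance would show itself. The plan works out what those patients will yield in tissue but names no toxicity count that obliges anyone to stop and look. Some DLTs under 5.2, such as Grade 3 fatigue lasting over a week, may not alarm singly; the signal is the running total. At stake is how many patients are treated at too high a dose before a review must take place.

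The blood-count mismatch bears on the same tally. Grade 4 neutropenia of 5 days or more is a DLT (5.2.3), and dropping the day 15 count makes it easier to miss.

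**Working it through.** **Inputs from the documents.** Cap 20, pair failure rate 40%, stop at 10 pairs, accrual 2-3 per month (13.3); MTD criterion of at most 1 of 6 (13.2); 21-day cycle 1 as DLT window (5.2, 6.2). **Assumptions.** The true DLT rate p, because no target rate is stated, and the DLT count at DL4, which is not given. Pairs and DLTs are taken as independent, with usability known at once.

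**1. The plan's own figure.** With X ~ Binomial(20, 0.6), P(X ≥ 10) = 0.872 and P(X ≥ 9) = 0.943. The stated 87% and 94% reproduce.

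**2. Expected size.** The 10th usable pair arrives at patient n with probability C(n−1, 9) × 0.6^10 × 0.4^(n−10) for n = 10 to 19; the remaining 0.186 falls on 20. The mean is 16.31. It would be 18.2 or 12.5 if 50% or 80% of pairs were usable.

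**3. Chance that a toxic dose passes.** P(≤1 of 6) = (1−p)^6 + 6p(1−p)^5 = 0.420, 0.351, 0.233 and 0.109 at p = 0.30, 1/3, 0.40 and 0.50. Declaring the MTD also needs the next level to fail. At p = 1/3 and 0.40, 16.31 expansion patients would have on average 16.31/3 = 5.4 and 16.31 × 0.40 = 6.5 DLTs.

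**4. Illustrative boundary.** Look after every 3 expansion patients and pause if cumulative cycle 1 DLTs, counting the first 6 patients, reach one third of the total: 3/9, 4/12, 5/15, 6/18, 7/21 or 8/24. One third is the 2-of-6 level at which 5.2 stops escalation. I used an exact recursion over (DLTs, usable pairs). It starts from 0 or 1 DLT in 6, weighted by (1−p)^6 and 6p(1−p)^5. Each patient adds a DLT with probability p and a usable pair with probability 0.6; accrual ends at 10 pairs or 20 patients.

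| True rate | P(pause), given ≤1 of 6 | after 0 of 6 | after 1 of 6 |
|---|---|---|---|
| 10% | 2% | 0.3% | 4% |
| 20% | 13% | 4% | 19% |
| 25% | 25% | 10% | 32% |
| 30% | 39% | 20% | 46% |
| 33% | 49% | 28% | 56% |
| 40% | 68% | 47% | 73% |
| 50% | 88% | 75% | 91% |

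Moving the usable rate from 50% to 80% changes P(pause) from 51% to 44% at p = 1/3, and from 14% to 12% at p = 0.20.

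**5. Upper bound on the saving.** If every pause closed the arm, mean size would be 11.55, 9.58 and 6.97 at p = 1/3, 0.40 and 0.50, against 16.31. Multiplying the difference by step 3:
- p = 1/3: 4.76 × 0.351 = 1.67 patients, 0.56 DLTs
- p = 0.40: 6.73 × 0.233 = 1.57 patients, 0.63 DLTs
- p = 0.50: 9.34 × 0.109 = 1.02 patients, 0.51 DLTs

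If enrolment continues at 2-3 per month while each patient's 21 days run (40,000 simulations), mean sizes become 12.2-12.5, 10.5-10.9 and 8.2-8.8. The same multiplication gives (16.31 − 12.5) × 0.351 = 1.3 to (16.31 − 12.2) × 0.351 = 1.4 patients at 1/3, likewise 1.3-1.4 at 0.40, and 0.8-0.9 at 0.50.

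**6. Day 15 blood count.** Assume a 5-day Grade 4 episode with onset uniform over days 8 to 22 and the next count on day 22. A count falls inside the episode with probability 5/14 = 36% without day 15 and 10/14 = 71% with it. A single count reveals the episode but cannot show that it lasted 5 days.

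**The case against.** Three stronger readings are tempting, and the documents support none of them.

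- *The expansion runs without safety oversight.* It does not. NCI would hear of serious DLTs quickly under 7.3.3, and the monitoring service receives data regularly. What is missing is only a count that makes a review compulsory.
- *The DLT definition contradicts the evaluability rule.* Section 5.1.1 counts a patient without DLT as evaluable if they "have received 90% of treatment doses for cycle one of therapy", while 5.2.7 says "Failure to tolerate 100% of the dosing in the first cycle will be considered a DLT". Arm B cycle 1 has 10 doses, so 9 of 10 might seem to satisfy both. But the opening definition in 5.2 requires an adverse event related to the drug, and 5.1.1 separates patients with a DLT from those who reached 90% without one. Nine of ten because of related toxicity is a DLT; nine of ten for another reason is evaluable without DLT; below 90% for a non-toxicity reason is replaced under 6.2.
- *The expansion has no DLT denominator.* Section 5.1.1 does limit its rule: "Patients are considered evaluable for toxicity for the purpose of arm dose escalation decisions". But 6.2 defines completion, replacement and evaluability for a cycle without restricting them to escalation, and 5.2 does not confine the DLT definition to escalation patients.

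The better objections concern size. The saving is small, and the illustrative trigger is not sharp: at 33% it pauses about half the time, and at 25% it pauses a quarter of the time. Timing also counts. The Arm B MTD was set by November 2016, some expansion patients were active by November 2017, and the adverse event list is dated May 2019. At 2-3 per month, 20 patients take 20/3 = 7 to 20/2 = 10 months, so much of the cohort may already have been treated. The documents do not give the number. These points limit the value of the change, but none supplies the missing count.

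**Conclusion.** The gap is real and narrow: general oversight exists, but no cumulative DLT count obliges a pause in Expansion Arm B. This is a low-cost improvement, not a flaw that undermines the trial. The benefit in step 5 is an upper bound, since it treats every pause as closure, and it depends on assumed true DLT rates of 33% or more, on the unknown DL4 result and on how many patients remained to be enrolled. The blood-count inconsistency stands separately: followed as written, 5.3.3 omits a day 15 count that two other sections require and weakens detection of one type of DLT.

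**What to change.** In 13.3, with a cross-reference in 5.2, add: after every 3 Expansion Arm B patients evaluable for cycle 1 DLT, new enrolment pauses for review by the principal investigator and CTEP if cumulative cycle 1 DLTs at this dose, including the first 6 patients, reach 3 of 9, 4 of 12, 5 of 15, 6 of 18, 7 of 21 or 8 of 24. The review records whether to resume, continue at the next lower level, or close. The team may prefer another boundary and should then quote its operating characteristics. Say that the 5.2 DLT definition and the evaluability rules in 5.1.1 and 6.2 apply to expansion patients, and that the tissue stop is subject to this pause. Section 5.2.7 needs no change.

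Separately, align 5.3.3 with Sections 5 and 10 by restoring the day 15 cycle 1 count.

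The cost is one paragraph, a sentence on scope, and at most one blood count per expansion patient beyond 5.3.3. No new committee is needed. The main downside is a pause that proves unnecessary, which the review can reverse by resuming accrual.
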